6.1 Population characteristics

Analysis for population characteristics will be performed on the SAF, unless otherwise specified.

6.1.1 Subjects Validity and Disposition

The number of subjects enrolled and included in each analysis set will be tabulated by region, country and center. The number of countries and study centers will be presented. A summary table will also be presented for the number of subjects enrolled and the number and percentage of subjects in each of the defined analysis sets. The reasons for subjects excluded from each of the analysis sets will also be tabulated. In addition, the number of subjects who were enrolled, treated and discontinued will be summarized. Reasons for discontinuation of study treatment will be tabulated. Important deviations will be summarized using frequency tables. These analyses will be performed on appropriate analysis sets like ‘All subjects assigned to treatment’ or ‘All enrolled subjects’.

6.1.2 Demographics and Other Baseline Characteristics

Summary statistics (arithmetic mean, standard deviation, median, minimum and maximum for quantitative variables) and frequency counts (for qualitative data) will be provided for demographics.

Demographics variables include sex, race, ethnicity, region, age in years (as reported in the CRF), weight, height and body mass index (BMI). If the PKS, MTD analysis set or EFS differ from the SAF, summary statistics and frequency tables for PKS and/or MTD analysis set and/or EFS will be provided as well.

Medical history findings will be summarized using MedDRA (Medical Dictionary for Regulatory Activities) terms (version 20.0 or later).

Cancer baseline characteristics will also be summarized. Variables include for example baseline Eastern Cooperative Oncology Group (ECOG) Performance Status, number of target lesions, number of non-target lesions, cancer type, histology, grade at initial diagnosis, stage at study entry, time since initial diagnosis. Please note that the list of the above mentioned parameters may not be exhaustive.

In addition, demographics (sex, race, ethnicity and age) and cancer baseline characteristics will be summarized for all subjects who signed the ICF for FGFR testing (“all enrolled subjects”).

6.1.3 Prior and Concurrent Medication/Therapy

Prior anti-cancer therapy and surgical therapeutic procedures will be summarized. The counts and percentages of subjects who were previously treated using radiotherapy, local anti-cancer therapy, systemic anti-cancer therapy, and who had any diagnostic and therapeutic procedure(s) will be presented. The number of subjects with radiotherapy and systemic or local anti-cancer therapy will be presented by intent of procedure and number of regimens/procedures. In addition, concurrent radiotherapy, diagnostic and therapeutic procedures will be summarized. Systemic anticancer therapy and type of systemic anticancer therapy during follow-up will be summarized. Immunotherapy during follow-up will be listed. Prior and concomitant medications will be coded to generic terms using the World Health Organization Drug Dictionary (WHO-DD) version 2005/Q3 or later and will be

provided in two tables, one for 'Prior medication' (i.e. medications that are ongoing at, or began before the start of study drug) and one for 'Concomitant medication' (i.e. medications that are ongoing at, or began after the start of study drug). The version used in analyses will be presented in the clinical study report.

6.1.4 Medical and Surgical History

Medical history findings will be summarized by primary system organ class, high level term and preferred term of MedDRA version 20.0 or later. The version used in analyses will be presented in the clinical study report.

6.2 Efficacy

Efficacy analyses will be performed on the EFS, unless otherwise specified.

All efficacy variables evaluated using the Response Evaluation Criteria in Solid Tumors (RECIST) version 1.1 are linked to the secondary and exploratory objectives of the study Part A. All variables evaluated using the Response Evaluation Criteria in Solid Tumors Modified for Immune-based Therapeutics (iRECIST) version 1.1 are exploratory only.

Efficacy data will be summarized using descriptive statistics and will be graphically displayed if appropriate. The correlation between pharmacodynamic parameters and selected safety, efficacy, or PK parameters may be graphically displayed. Further statistical analyses may be conducted.

Response as defined by RECIST version 1.1: complete response (CR), partial response (PR), stable disease (SD), progressive disease (PD). Response and progression will be evaluated in this trial using the new international criteria proposed by the RECIST committee for solid tumor.

iRECIST defines new response categories, including iUPD (unconfirmed progressive disease) and iCPD (confirmed progressive disease). For purposes of iRECIST assessment, the first visit showing progression according to RECIST 1.1 will be assigned a visit (overall) response of iUPD, regardless of which factors caused the progression.

Best overall tumor response according to RECIST criteria will be summarized using frequency counts. Best % change in Target Lesion sum of diameter from baseline will be displayed graphically for all subjects from worst to best in a waterfall plot.

6.2.1 Primary Efficacy Variable

Not applicable.

6.2.2 Secondary Efficacy Variable

The efficacy variable linked to the secondary objective of this study is the objective response rate.

Objective response rate (ORR) is defined as the percentage of subjects whose best response is either a CR or PR. Subjects for whom best tumor response is not CR or PR, as well as subjects without any efficacy assessment will be considered non-responders. According to RECIST version 1.1, confirmation of PR and CR is not required considering the nature of the study and the protocol requirements.

6.2.3 Exploratory Efficacy Variables

Exploratory efficacy variables defined according to RECIST version 1.1 will include disease control rate (DCR), duration of response (DOR), progression-free survival (PFS) (according to both RECIST and iRECIST), time to progression (TPP), time to response (TTR), overall survival (OS) and follow-up time.

These variables are defined as below:

Follow-up time is defined as the time from the date of first study treatment until death or the date of last contact, if the subject is still alive at the time of analysis.

Disease control rate (DCR) is defined as the percentage of subjects whose overall best response was not progressive disease (i.e. CR, PR, SD or Non CR/Non PD). Tumor assessments with SD as response, that is performed prematurely after assignment to treatment of the subject (i.e. substantially earlier than the first planned radiological tumor assessment at 9 weeks), will not be taken into account.

Duration of response (DOR) (for PR and CR) is defined as the time (days) from the first documented objective response of PR or CR, whichever is noted earlier, to disease progression or death (if death occurs before progression is documented). DOR will be defined for responders only, i.e. subjects with a CR or PR. The actual dates the tumor scans were performed will be used for this calculation. DOR for subjects who have not progressed or died at the time of analysis will be censored at the date of their last tumor assessment.

Kaplan-Meier (KM) product-limit estimates for median, 25th and 75th percentile with its 95% CI together with total number of subjects, total censored and total events will be provided for DOR per dose group. In addition KM survival curves will be presented for each dose group.

Progression-free survival (PFS) is defined as the time (days) from start of study treatment to date of first observed disease progression (investigator's radiological or clinical assessment) or death due to any cause, if death occurs before progression is documented. The actual date that the tumor scan was performed will be used for this calculation. If a tumor assessment is performed over more than one day (e.g. scans for chest and abdomen done on different days for the same evaluation), the earliest date will be used for the calculation of PFS. For subjects without documented radiological or clinical progression or death at the time of analysis, PFS will be censored at the last actual visit date of tumor evaluation.

Kaplan-Meier (KM) product-limit estimates for median, 25th and 75th percentile with its 95% CI together with total number of subjects, total censored and total events will be provided for PFS per dose group. In addition KM survival curves will be presented for each dose group.

Overall survival (OS) is defined as the time (days) from start of study treatment to death due to any cause. Subjects alive at the date of data cut-off for analysis will be censored at the last date known to be alive. If a subject is lost to follow-up before any assessment after assignment to treatment, this subject will be censored at day 1.

KM product-limit estimates for median, 25th and 75th percentile with its 95% CI together with total number of subjects, total censored and total events will be provided for OS per dose group. In addition KM survival curves will be presented for each dose group.

Time to progression (TTP) is defined as the time (days) from start of study treatment to date of first observed disease progression (radiological or clinical). TTP for subjects without disease progression at the time of analysis will be censored at the last date of tumor evaluation. TTP for subjects who have no tumor assessments after baseline will be censored at day 1.

KM product-limit estimates for median, 25th and 75th percentile with its 95% CI together with total number of subjects, total censored and total events will be provided for TTP. In addition KM survival curves will be presented for each dose group.

Time to Response (TTR) is defined as the time (days) from start of study treatment to the date of first observed partial or complete response. Only subjects with a partial or complete response are considered for TTR.

KM product-limit estimates for median, 25th and 75th percentile with its 95% CI together with total number of subjects, total censored and total events will be provided for TTR. In addition KM survival curves will be presented for each dose group.

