Cohort 1 of IMvigor210 comprised patients who had not received previous treatment in the metastatic setting and were judged to be ineligible for cisplatin treatment. 123 patients were enrolled, of whom 119 received one or more doses of atezolizumab. At 17.2 months' median follow-up, the objective response rate was 23% and the complete response rate was 9%. Median response duration was not reached. Response occurred across all PD-L1 and poor prognostic factor subgroup. Median PFS was 2.7 months and median overall survival was 15.9 months. Tumor mutation load was associated with response. Treatment-related adverse events that occur in 10% or more of patients were fatigue (30%), diarrhea (12%), and pruritus (11%). One treatment-related death (sepsis) occurred. Nine (8%) patients had an adverse event leading to treatment discontinuation. Immune-mediated events occurred in 12% patients (18).

Details of ongoing and completed studies with atezolizumab can be found in the latest available version of the IB for atezolizumab. The IB in its most current version is available in the study file.

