5.6 Primary completion

As safety is the primary objective of Part A, the primary completion event for Part A will be its LPLV or 9 months after LPFV, whichever occurs first.

The primary completion date for this study according to the FDA Amendment Act is specified in a separate document (not part of this study protocol).

6. Study population

Eligible patients for this study will be patients with locally advanced or metastatic urothelial carcinoma, who are cisplatin-ineligible and have had no prior systemic treatment for locally advanced or metastatic disease.

Patient eligibility will be checked at two sequential time points:

1. At FGFR testing:

- FGFR testing of patients will be performed at the investigators' discretion prior to start of screening (i.e. before signing of informed consent for study treatment eligibility).
- Besides the basic criteria for FGFR testing specified below, any criterion as outlined under inclusion and exclusion criteria for screening already known to prohibit the patient's participation in the study should be considered. Investigators should ensure all patients will be eligible in terms of clinical condition, disease status and lines of treatment. For "FGFR testing failure" (those that are FGFR test negative and/or those that do not meet the inclusion/exclusion criteria) see Section 11.1.

2. At screening:

• FGFR1 or 3 positive patients (RNAscope score of 3+ or 4+) will be checked for final eligibility using all further selection criteria specified below. For "screening failure" see Section 11.1

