4.1 General Principles

The statistical evaluation will be performed by using the software package SAS release 9.2 or higher (SAS Institute Inc., Cary, NC, USA).

All variables will be analyzed by descriptive statistical methods. The number of data available and mean, standard deviation, minimum, median, and maximum will be calculated for metric data. Frequency tables will be generated for categorical data.

Due to the exploratory character of this Part A of the study, no confirmatory analysis will be performed. All calculated p-values and confidence intervals are to be interpreted in the exploratory sense.

Data displays will follow the standard table catalogs for oncology standards, global standards, and clinical pharmacology standards, respectively.

All summaries will be performed by dose group. The dose groups “Rogaratinib XX mg BID+ Atezolizumab” will be analyzed, in which “XXmg” stands for the assigned dose. Pooled summary statistics (or frequency counts) will be provided where appropriate. Listings will also be provided by dose group.

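### SAP 6.2.3 ends follow-up time at death, so its plain median understates potential survival follow-up and should be relabelled and supplemented by a reverse Kaplan-Meier median for OS

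*SAP*

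**What the plan says.** SAP 6.2.3 lists follow-up time among the exploratory efficacy variables: "Follow-up time is defined as the time from the date of first study treatment until death or the date of last contact", with last contact used only for subjects alive at analysis. The document history in SAP section 7 shows that the definition was added in the Supplement of 05 APR 2022. Protocol 10.3.3.2 has no such variable.

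DOR, PFS, OS, TTP and TTR each get a Kaplan-Meier sentence in SAP 6.2.3. Follow-up time gets none, and no other statistic is named for it. The general rule in SAP 4.1 then applies: "The number of data available and mean, standard deviation, minimum, median, and maximum will be calculated for metric data". The same section asks for all summaries by dose group.

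The neighbouring definitions matter here:

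- OS runs from start of treatment to death. For the rest, "Subjects alive at the date of data cut-off for analysis will be censored at the last date known to be alive".
- DOR starts at first response and, without progression or death, "will be censored at the date of their last tumor assessment".
- Without an event, "PFS will be censored at the last actual visit date of tumor evaluation".

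Neither document provides for a reverse Kaplan-Meier estimate, time to data cut-off, or follow-up among survivors only.

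**The concern.** Apart from the day-1 rule for subjects lost before any assessment, this variable is the OS time with the event indicator removed. Its plain median counts a death at month 6 and a loss of contact at month 6 as the same thing. It therefore estimates neither survival nor how long patients could have been observed.

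Readers commonly use a median follow-up figure to judge whether survival data are mature. Here the figure would be too low, and it would move with mortality. Better survival would lengthen it with no further observation. A dose group with more early deaths would look less well followed than another group observed for just as long.

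**Working it through.** The plan gives no follow-up figure, target follow-up or expected number of deaths, so there is nothing to reproduce. What can be checked is the behaviour of the stated rule.

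**Inputs**

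- Median OS *m*. Protocol 3.4 reports for the first-line, cisplatin-ineligible atezolizumab cohort: "Median PFS was 2.7 months and median overall survival was 15.9 months". I use 15.9 months as an illustration and 9 to 24 months as an assumed range, with exponential survival, S(t) = 2^(−t/m).
- Potential follow-up *C*, uniform between *a* and *b* months. This is an assumption. The only anchor is Protocol 5.6, under which "the primary completion event for Part A will be its LPLV or 9 months after LPFV, whichever occurs first". No accrual period is given.

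**Formula.** The SAP variable is Y = min(T, C), with T the time to death. With T and C independent, P(Y > t) = S(t) × P(C > t). The median of Y is the t at which this product equals 0.5. Since P(C > t) ≤ 1, the population median of Y cannot exceed *m*. Since S(t) < 1, it lies below the median of C.

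**Example 1: m = 15.9, C uniform on 9–27.** At t = 11.9:

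- S = 2^(−11.9/15.9) = 0.595
- P(C > 11.9) = (27 − 11.9)/18 = 0.839
- product = 0.50

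The SAP median is 11.9 months. Median potential follow-up is (9 + 27)/2 = 18.0. The shortfall is 6.1 months.

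**Example 2: m = 15.9, C uniform on 24–36.** Everyone could be observed past 15.9 months, so P(Y > 15.9) = 0.5 × 1 and the SAP median is 15.9. Median potential follow-up is 30.0. If the window moves to 36–48, the SAP median stays at 15.9 while potential follow-up rises to 42.0.

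**Range.** SAP median in months, by window. Simulation with 200,000 subjects per cell agrees to within 0.1.

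| Median OS | 9–18 | 9–27 | 24–36 | 24–48 | 36–48 |
|---|---|---|---|---|---|
| 9 | 9.0 | 9.0 | 9.0 | 9.0 | 9.0 |
| 12 | 10.0 | 10.5 | 12.0 | 12.0 | 12.0 |
| 15.9 | 10.8 | 11.9 | 15.9 | 15.9 | 15.9 |
| 24 | 11.7 | 13.7 | 24.0 | 24.0 | 24.0 |
| **Potential follow-up, median** | **13.5** | **18.0** | **30.0** | **36.0** | **42.0** |

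The smallest shortfall is 13.5 − 11.7 = 1.8 months and the largest is 42.0 − 9.0 = 33.0 months. Reverse Kaplan-Meier on the same simulated data (deaths censored, end of contact alive as the event) returned the bottom row to within 0.1.

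**Sensitivity**

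- Last contact up to 3 months before cut-off (Protocol 5.2.3 plans survival contacts about every 3 months), m = 15.9, window 9–27: SAP median 11.0, reverse Kaplan-Meier 16.9.
- Trial-sized samples, m = 15.9, window 24–36: the SAP median was below the reverse Kaplan-Meier median in more than 99% of simulated trials, both with 26 and with 30 subjects.

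**PFS and DOR.** Take 9-week scans (2.07 months), response at the first or second scan, and censoring up to one scan interval before cut-off. Median potential follow-up is then:

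| Window | OS | PFS | DOR | SAP median (m = 15.9) |
|---|---|---|---|---|
| 9–18 | 13.5 | 12.5 | 9.4 | 10.8 |
| 9–27 | 18.0 | 17.0 | 13.9 | 11.9 |
| 24–36 | 30.0 | 29.0 | 25.8 | 15.9 |

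For DOR the direction is not fixed: in the 9–18 window the SAP median lies above potential DOR follow-up.

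**The case against.** The definition is clear and computable, and the SAP never calls it a measure of maturity. Read as observed time on study, it is a legitimate description, and the plain median is only implied by SAP 4.1. Maturity is also documented elsewhere: "total number of subjects, total censored and total events will be provided for OS per dose group", with matching wording for PFS and DOR, plus quartiles with confidence intervals and Kaplan-Meier curves. The variable is exploratory, drives no decision, and errs towards making OS look less mature. All of this stands, and it makes this a minor point. It does not make the figure a measure of follow-up, which is what its name promises.

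A reader might infer that the figure understates follow-up for PFS and DOR in the same way. The documents do not support that as a general statement. Both endpoints are censored at the last tumor assessment and DOR starts at response, so time to last contact is the wrong clock for them whether or not death stops it. For the same reason, reverse Kaplan-Meier on the OS data would overstate their follow-up (18.0 against 17.0 for PFS and 13.9 for DOR in the 9–27 window).

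A reader might also set the result beside the 17.2-month median follow-up that Protocol 3.4 gives for the atezolizumab cohort. The protocol does not say how that figure was calculated, and neither document plans the comparison, so it cannot support this point.

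**Conclusion.** The point holds for survival follow-up. As defined, the median blends mortality with length of observation, its population value is capped by median OS, and it understates potential OS follow-up when subjects die. It equals median OS only when every subject could be observed beyond that median; otherwise it lies below both median OS and potential follow-up.

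The direction is certain, but the size is not. A shortfall of about 2 to 33 months follows from assumed exponential survival and assumed uniform windows. No single value can be claimed for this trial. The remark in Protocol 15.3 that remaining patients had been on treatment for at least 2 years describes only those still on treatment and does not fix the window.

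Nor should a reader conclude that any efficacy result is biased: the OS, PFS and DOR estimates do not use this variable.

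**What to change.** In SAP 6.2.3:

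1. Report median follow-up for OS by reverse Kaplan-Meier, with deaths censored and last contact alive as the event.
2. Relabel the present variable as time on study and keep it, if wanted, as a descriptive line.
3. If follow-up is quoted for PFS or DOR, apply reverse Kaplan-Meier to that endpoint's own time origin and last-tumor-assessment censoring.

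The cost is a sentence or two in the SAP and one line of code to reverse the event indicator. No new data are needed, because the OS analysis already requires the dates of death and of last contact alive.

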To facilitate an independent evaluation of outcome in this study, tumor assessment imaging data will be collected, image quality controlled and stored for a potential central review of tumor evaluation by independent readers prior to the final efficacy analysis. The decision to perform the central review will be based on the outcome of the local efficacy assessments. Treatment decisions with immune-based therapeutics require assessment of the clinical presentation of patients that can only be performed by the investigator; therefore, central review will not be used for treatment decisions. Details will be outlined in the Image Review Charter. Images for tumor assessment, de-identified with respect to patient identification related privacy data (except study related subject identification number) will be collected for all patients enrolled at baseline and at all post-baseline evaluations and will be submitted for collection and image quality control to facilitate a potential central review. Specific information on image handling, imaging guidelines, instructions for image acquisition and image evaluation procedures will be outlined in the Imaging Manual for the study sites.

The first radiological tumor evaluation will be conducted during clinical screening within 28 days before start of study treatment (see Section 9.1). Tumor assessments are to be done every 9 weeks (± 7 days) starting from Cycle 1 Day 1 until radiological disease progression or end of the study. A minimum of at least 9 weeks from start of treatment is mandatory for the 1st "on treatment" tumor assessment.

For patients who discontinue study treatment without radiological disease progression, follow-up tumor evaluations will be performed (by CT or MRI) until progression of malignancy and/or start of subsequent systemic anti-cancer treatment, whichever comes first, or any other criterion for withdrawal is met. During the active follow-up period, CT/MRI evaluations will be performed every 9 weeks (from the previous scan date). After 1 year of follow-up, CT scans may be scheduled approximately every 12 weeks. After primary completion, no tumor assessments will be done.

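### SAP 6.2.3: the day-1 censoring sentence for TTP has no without-progression condition, so read literally it censors a clinical progression that was never scanned

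*SAP*

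**What the plan says.** TTP is defined only in SAP 6.2.3; Protocol 10.3.3.2 does not list it. The SAP text has three parts:

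- **Event.** TTP runs from start of treatment to the "date of first observed disease progression (radiological or clinical"). Clinical progression therefore counts without a scan.
- **General censoring.** "TTP for subjects without disease progression at the time of analysis will be censored at the last date of tumor evaluation". This applies only to subjects without progression.
- **Special case.** "TTP for subjects who have no tumor assessments after baseline will be censored at day 1". The only condition is the absence of a scan.

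In the same section, the PFS event is "first observed disease progression (investigator's radiological or clinical assessment) or death due to any cause". PFS censoring states who it covers, "For subjects without documented radiological or clinical progression or death at the time of analysis", and when: "PFS will be censored at the last actual visit date of tumor evaluation". PFS has no rule for a subject with no post-baseline evaluation. OS has one: "If a subject is lost to follow-up before any assessment after assignment to treatment, this subject will be censored at day 1".

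Efficacy analyses use the efficacy analysis set (EFS). SAP 5.1 requires at least one dose and some post-baseline efficacy data, without saying what counts as such data. On timing, Protocol 9.4 says "A minimum of at least 9 weeks from start of treatment is mandatory for the 1st" on-treatment scan, and places the baseline scan up to 28 days before first dose.

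**The concern.** The event definition and the special-case sentence give different answers for one kind of subject: clinical progression, no scan after baseline. The first makes the progression an event on its date. The second, taken on its own words, removes the subject from the risk set at day 1. PFS counts the same progression as an event, so two endpoints meant to agree on progression would disagree for the same subject.

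The error would run one way. The subjects affected would be mainly early progressors, and turning their events into censored observations with almost no follow-up lengthens TTP. A programmer following the sentence literally would produce this with no sign in the output that progressions had been dropped.

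A smaller point concerns PFS. TTP and OS have a day-1 floor and PFS does not. For a subject who is alive, unprogressed and unscanned after baseline, the last tumor evaluation is the screening scan, which predates treatment.

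**Working it through.** The documents give no figure for TTP or PFS, so there is no stated result to reproduce. The check has four steps.

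**1. Literal application.** Take clinical progression on day 35 with no post-baseline scan. PFS: event at day 35. TTP by its event definition: event at day 35. TTP by the special-case sentence: censored at day 1. By contrast, RECIST progression on a day-63 scan gives an event at day 63 for both endpoints. The conflict is confined to unscanned clinical progressors.

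**2. Can the group arise?** The first scheduled on-treatment scan comes no earlier than 9 weeks (63 days). Clinical progression ends treatment (Protocol 7.4.4). An end-of-treatment scan is then due within 14 days, but up to week 18 it is not needed if the previous scan was within 4 weeks (Protocol 9.2.2.5; Table 9-2, footnote q). With a baseline scan b days before first dose and an end-of-treatment visit d days after it, the waiver covers b + d up to 28. For example, b = 7 and d = 14 (assumed values) give 21, so no scan is required. In active follow-up, scans stop once new systemic therapy starts (Protocol 5.2.3). The group can therefore arise without a protocol deviation, though only early. The day-35 subject in step 1 has a baseline scan at least 35 days old and would need to have missed a required scan.

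**3. Size.** Inputs: n = 26 (the minimum evaluable number in Protocol 10.4); k = number affected (assumed). With no other censoring and k subjects removed at day 1, the curve after the last of those k progressions is

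S_literal(t) = (number progression-free at t)/(26-k) = S_correct(t) x 26/(26-k).

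k = 1: 26/25 = 1.040. k = 2: 26/24 = 1.083. k = 3: 26/23 = 1.130. With other censoring the factor is approximate.

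As an illustration, 26 event times were placed at exponential quantiles, and the k earliest were treated either as events or as censored at day 1. The 2.7-month median is the PFS median for atezolizumab alone quoted in Protocol 3.4; 4 and 6 months are assumed alternatives.

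| Assumed median (months) | Quantity | k = 0, or events kept | k = 1 | k = 2 | k = 3 |
|---|---|---|---|---|---|
| 2.7 | KM median (months) | 2.55 | 2.85 | 2.85 | 3.18 |
| 2.7 | KM at day 63 | 15/26 = 0.577 | 15/25 = 0.600 | 15/24 = 0.625 | 15/23 = 0.652 |
| 4 | KM median (months) | 3.78 | 4.23 | 4.23 | 4.71 |
| 4 | KM at day 63 | 18/26 = 0.692 | 18/25 = 0.720 | 18/24 = 0.750 | 18/23 = 0.783 |
| 6 | KM median (months) | 5.67 | 6.34 | 6.34 | 7.06 |
| 6 | KM at day 63 | 20/26 = 0.769 | 20/25 = 0.800 | 20/24 = 0.833 | 20/23 = 0.870 |

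The k = 0 medians fall slightly below the assumed values because the curve steps at 26 discrete points.

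**4. PFS without a floor.** A baseline scan 28 to 1 days before first dose gives a censoring time of -28 to -1 days. Replacing such a time with day 1 leaves the Kaplan-Meier curve unchanged as long as no event has occurred by day 1, because either way the subject leaves before the first drop. A direct comparison of day -14 with day 1, for 1, 2 and 3 such subjects of 26, gave identical curves.

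**The case against.** The strongest reply is that the special-case sentence directly follows one limited to subjects without progression, and is most naturally read as supplying their censoring date when there is no later scan. On that reading a clinical progressor was already an event and never reaches the rule. This reading is open and may be what was intended. But the text does not say so, the PFS rule in the same section shows the condition can be written out, and no protocol definition of TTP settles the matter.

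Second, the EFS may exclude unscanned subjects. That depends on an undefined term. Clinical progression plausibly counts as post-baseline efficacy data, and if every unscanned subject were excluded, the special-case sentence would apply to nobody. SAP 6.2.2 also counts subjects without any efficacy assessment as non-responders, which suggests that some are expected in the analysis.

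Third, the end-of-treatment scan, and the repeat scan that Protocol 9.4 advises when progression is suspected, shrink the group. This stands: k may be small or zero. A reader might point out that an exponential curve with a 2.7-month median puts 1 - 2^(-63/(2.7 x 30.44)) = 41% of PFS events before day 63. That figure comes from another trial's PFS, where deaths also count and progression may be found on a scan. It says early events are common, not how many go unscanned.

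Fourth, no decision rests on TTP. This also stands and limits the severity.

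**Conclusion.** The TTP censoring text is ambiguous and, on its literal reading, contradicts the TTP event definition. The error can only lengthen TTP: about +4%, +8% or +13% on the later curve for k = 1, 2 or 3 of 26. This rests on the literal reading, on affected subjects being in the EFS, and on an assumed k. At k = 0 there is no effect.

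Two stronger conclusions are tempting and not supported. A reader might infer that TTP will be inflated; the documents support only that it could be, since the other reading is open and k is not given. A reader might also infer that PFS censors unscanned subjects before treatment starts and so distorts the PFS curve. Unscanned subjects who progress clinically or die are PFS events. The pre-treatment date is an inference from a missing rule, not something the SAP states. The EFS may exclude the remaining subjects, and the Kaplan-Meier estimate is the same either way. What remains is a possible negative time whose handling is unstated.

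Severity is low. TTP and PFS are exploratory, no confirmatory analysis is planned, dose selection rests on DLTs, and the sample-size reasoning rests on response rate.

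**What to change.** In SAP 6.2.3, replace the special-case sentence with: *TTP for subjects with neither a tumor assessment after baseline nor documented radiological or clinical progression will be censored at day 1.*

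For consistency, add to PFS: *EFS subjects who are alive, without radiological or clinical progression and without a tumor assessment after baseline will be censored at day 1.*

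It would also help to state in SAP 5.1 whether clinical progression or survival status alone counts as post-baseline efficacy data, since that decides whether either rule applies to anyone.

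The cost is one clause for TTP and one sentence for PFS, with no new data. TTP may come out slightly less favourable than under the literal rule; the PFS estimate does not change.
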